8.4 Parent Study Safety Analysis Period

The safety analysis period will be the same as Treatment-emergent period defined in the SAP/CSR for Study 106.

9 STATISTICAL ANALYSIS

9.1 General Considerations

Continuous variables will be summarized using the following descriptive summary statistics: the number of subjects (n), mean, standard deviation (SD), median, minimum value (min), and maximum value (max).

Categorical variables will be summarized using counts and percentages.

Visit Windowing Rules: [Section 11.1](#) defines the windows for protocol-defined visits. Note, spirometry assessments, BMI, weight, and height will be used for both efficacy and safety purposes. Their measurements will follow the visit windowing rules for efficacy parameters.

The windows will be applied for both scheduled and unscheduled visits. If no measurement is available within a visit window, the assessment will be considered missing for the visit. If there is more than one measurement available within the same visit window, the following rules will be used:

For all safety parameters, if there are multiple measurements within a visit window, then

- The record closest to the target day will be used, with the exception of the threshold analysis in which the worst record will be used.
- If there are multiple records within the same distance of the target day, the latest record will be used.
- The SFU visit will not be windowed; instead, the nominal visit will be used in relevant analyses.

For all efficacy parameters, if there are multiple measurements within a visit window, the record at the scheduled visit will be used. Otherwise,

- If there are multiple records with the same distance to the target day, the latest record will be used.
- If there are no measurements at the scheduled visit, then the record closest to the target day will be used.

- Assessments at the Early Treatment Termination (ETT) Visit will follow the windowing rules for regular visits.
- Assessments at SFU Visit will follow the windowing rules for regular visits if they fall within the upper boundary of the window for the last scheduled visit. If assessments occur after the upper boundary of the window for the last scheduled visit, they will be still considered as the SFU Visit.

Incomplete/Missing data will not be imputed, unless otherwise specified.

Outliers: No formal statistical analyses will be performed to detect or remedy the presence of statistical outliers, unless otherwise specified.

Unscheduled **Visits:** Unscheduled visit measurements will be included in the following:

- Derivations of measurements at scheduled visits per specified visit windowing rules;
- Derivations of baseline/last on-treatment measurements;
- Derivations of the maximum/minimum on-treatment values and maximum/minimum changes from baseline values for safety analyses;
- Data listings where appropriate.

Treatment-emergent (TE) Period will include the time from the first active dose of VX-661/ivacaftor or ivacaftor alone (in the parent study or Study VX14-661-110, but after the washout period, if applicable) to the Safety Follow-up Visit in Part A or 28 days after the last dose of the study drug for subjects who do not have a Safety Follow-up Visit or who have their Safety Follow-up Visit more than 35 days after the last dose in Part A of Study VX14-661-110. For subjects who participate in another qualified Vertex study before completing Part A of Study VX14-661-110 (96 weeks) and re-enroll in Study VX14-661-110, the TE Period will exclude the time spent in the other study.

110 Treatment-Emergent (TE) Period is defined as the time from 1st dose of study drug in Part A to SFU in Part A or 28 days after the last dose of the study drug for subjects who do not have a SFU Visit or who have their SFU Visit more than 35 days after the last dose in Part A. For subjects who participate in another qualified Vertex study before completing Part A (96 weeks) and re-enroll in Study 110, the TE Period will exclude the time spent in the other study. The **efficacy analysis baseline** is defined as the most recent non-missing measurement (scheduled or unscheduled) collected prior to the first dose of study drug in the parent studies for all subjects, except for subjects randomized to the placebo arm in Study 106.

The efficacy analysis baseline for subjects randomized to the Study 106 placebo arm is defined as the most recent non-missing measurement (scheduled or unscheduled) collected prior to the first dose of study drug in Study 110.

The **safety analysis baseline**, unless otherwise specified, is defined as the last non-missing assessment prior to the first dose of active treatment (TEZ/IVA or IVA) from the parent study (after the wash-out period, where applicable) or Study 110, whichever is earlier.

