12.3 Statistical Analysis

12.3.1 General Considerations

Continuous variables will be summarized using the following descriptive summary statistics: the number of subjects (n), mean, SD, median, minimum value (min), and maximum value (max).

Categorical variables will be summarized using counts and percentages.

Baseline value, unless otherwise specified, for efficacy and safety analyses, will be defined as the most recent non-missing measurement (scheduled or unscheduled) collected before the first dose of VX-661/ivacaftor or ivacaftor alone (in the parent study or Study VX14-661-110, but

after the washout period, if applicable). For subjects who received VX-661 and ivacaftor combination therapy in the parent study, the baseline will be the same as the baseline in the parent study. For subjects who received placebo or ivacaftor in the parent study and transitioned to VX-661/ivacaftor in Study VX14-661-110, the baseline will be the baseline in Study VX14-661-110. For subjects from Study VX14-661-108, the parent study baseline will be the baseline for Treatment Period 2 in Study VX14-661-108. For subjects from Study VX13-661-103, the parent study baseline will be the baseline in the Open-label Phase of Study VX13-661-103 for subjects who participated in the Open-label Phase or the baseline in Study VX14-661-110 for subjects who did not participate in the Open-label Phase of Study VX13-661-103.

Change (absolute change) from baseline will be calculated as postbaseline value - baseline value.

Relative change from baseline will be calculated as (postbaseline value - baseline value)/baseline value.

Efficacy Analysis Period will include the time from the first dose of VX-661/ivacaftor or ivacaftor alone (in the parent study or Study VX14-661-110, but after the washout period, if applicable) to the last scheduled efficacy visit in Part of Study VX14-661-110. For subjects who participate in another qualified Vertex study before completing Study VX14-661-110 assessments and re-enroll in Study VX14-661-110, the Efficacy Analysis Period will exclude the time between the last dose before the discontinuation from Study VX14-661-110 and the first dose after re-enrollment in Study VX14-661-110.

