12.3.2 Overview of Analysis Strategies

- Study VX14-661-110 data will not be analyzed in isolation as patients received different durations of treatment in the parent studies. Study VX14-661-110 data will be integrated with the parent study data for each subject from the first active dose of VX-661/ivacaftor or ivacaftor alone (after the washout period, if applicable).
- The analysis baseline will be the last non-missing measurement prior to the first active dose of VX-661/ivacaftor or ivacaftor alone [in the parent study (after the washout period, if

applicable) or Study VX14-661-110]. All post-baseline measurements will be mapped to the uniform analysis visit windows based on the study days counted from the first active dose of VX-661/ivacaftor or ivacaftor alone (after the washout period in the parent study, if applicable) to make the results more comparable and interpretable.

- For subjects in Study VX14-661-110, the safety analyses will be performed on all of the subjects pooled together. The efficacy analysis will be performed on each CFTR mutation group separately (*F508del/F508del*, *F508del/Residual Function*, and *F508del/Gating*).

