8.2 Pulmonary Exacerbation Analysis Period

PEx Efficacy Analysis Period is defined as the time period from the first dose of TEZ/IVA in parent study (after the washout period, if applicable) or Study 110 Part A to the date of last efficacy assessment in parent study or Study 110 Part A, as highlighted in grey in [Table 8-1](#). Note for parent Study 108, only Period 2 is pooled.

Similarly, for subjects who participate in another qualified Vertex study before completing Study 110 assessments and re-enroll in Study 110, the PEx Efficacy Analysis Period will exclude the time between the last dose before the discontinuation from Study 110 and the first dose after re-enrollment in Study 110.

Table 8-1 PEx Analysis Period for PEx Analysis Sets			
Analysis Set	Analysis Period		
	Parent Study		Study 110 Part A
106/110 PEx Analysis Set	TEZ/IVA		TEZ/IVA
	PBO		TEZ/IVA
108/110 PEx Analysis Set	Period 1: TEZ/IVA	Period 2: IVA	TEZ/IVA
	Period 1: IVA	Period 2: TEZ/IVA	TEZ/IVA
	Period 1: TEZ/IVA	Period 2: PBO	TEZ/IVA
	Period 1: PBO	Period 2: TEZ/IVA	TEZ/IVA

	Period 1: IVA	Period 2: PBO	TEZ/IVA
	Period 1: PBO	Period 2: IVA	TEZ/IVA

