9.6.2.1.2 Subjects in 108/110 ES

The analysis for 108/110 ES during 110 Efficacy Analysis Period will be similar to that for 106/110 ES with the exception of different fixed effects: treatment (PBO-TEZ/IVA, IVA-TEZ/IVA, TEZ/IVA), visit, treatment-by-visit interaction and parent study baseline ppFEV₁.

Similarly, the results from this MMRM along with descriptive statistics for observed values and absolute changes from baseline will be presented at scheduled visits within each treatment

group, and LS means ($\pm 95\%$ CI) for absolute change from baseline at each visit will also be plotted by treatment group.

9.6.2.1.3 Subjects in FAS Who Roll Over from Study 103

For FAS patients rolling over from Study 103, descriptive statistics will be summarized for observed values and absolute changes from baseline in ppFEV₁ by treatment group at scheduled visit during 110 Efficacy Analysis Period.

9.6.2.1.4 Subjects in FAS Who Roll Over from Study 111

The analysis for FAS patients rolling over from Study 111 will be similar to that for FAS patients rolling over from Study 103.

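### Does the SAP's efficacy baseline for Study 108 and Study 103 rollovers, which differs from the protocol's, need to change?

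*SAP*

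**What the plan says.** **SAP.** Section 9.1 sets the efficacy baseline at the most recent non-missing value "prior to the first dose of study drug in the parent studies for all subjects, except for subjects randomized to the placebo arm" of Study 106; that arm takes its last value before Study 110 dosing. No Study 108 period or Study 103 phase is named. The safety baseline in the same section is keyed differently, to the last value "prior to the first dose of active treatment (TEZ/IVA or IVA) from the parent study (after the wash-out period, where applicable"; the Study 110 dose counts instead where it came first. Section 7.1 groups Study 108 rollovers by their Period 2 treatment, and section 8.2 restricts the exacerbation analysis: "Note for parent Study 108, only Period 2 is pooled". The ppFEV1 model in section 9.6.2.1.2 has as fixed effects treatment, "visit, treatment-by-visit interaction and parent study baseline" ppFEV1, again with no period named.

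**Protocol.** Section 12.3.1 gives a general rule based on the first dose of VX-661/ivacaftor (TEZ/IVA in the SAP) or of ivacaftor alone, then adds specific rules. For those who had "received placebo or ivacaftor in the parent study and transitioned to VX-661/ivacaftor in Study VX14-661-110, the baseline will be the baseline in Study VX14-661-110". The Study 108 rule is: "For subjects from Study VX14-661-108, the parent study baseline will be the baseline for Treatment Period 2 in Study VX14-661-108". In Study 103, "the parent study baseline will be the baseline in the Open-label Phase of Study VX13-661-103" if the subject took part in that phase, and otherwise the Study 110 baseline. Section 12.3.2 repeats the general rule: "The analysis baseline will be the last non-missing measurement prior to the first active dose of VX-661/ivacaftor or ivacaftor alone".

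**The concern.** In a crossover, the first dose of study drug in the parent study is literally the first Period 1 dose, whereas the protocol names Period 2. The SAP's treatment-emergent period, exacerbation period and safety baseline all refer to the washout; only the efficacy baseline does not, which could suggest an oversight. The SAP resets the baseline to Study 110 for Study 106 placebo subjects but not for Study 108 placebo subjects, so the label PBO-TEZ/IVA has a different origin in the two sets of outputs. The covariate's period is defined only in the protocol, so a programmer could pair a Period 2 covariate with a change score that starts before Period 1.

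At stake is the meaning of the reported means. If the protocol's rule for ivacaftor rollovers governed, the IVA-TEZ/IVA change would be the gain over ivacaftor. Under the SAP it is the whole gain from before any study drug, and no planned output shows the gain over ivacaftor separately.

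**Working it through.** **Counts (SAP 6.2).** 23 + 464 + 159 + 227 + 138 + 33 = 1,044, the stated total. The two documents' rules differ for up to 227 + 23 = 250 subjects: 250/1,044 = 23.9% of enrolment, or 250/747 = 33.5% of the four studies with efficacy summaries (464 + 227 + 23 + 33 = 747).

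**What each rule gives an IVA-TEZ/IVA subject.** Let B1, B2 and B3 be the values before Period 1, Period 2 and Study 110, and Y a Study 110 visit value. B3 is measured on ivacaftor.

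| Rule | Change | Meaning |
|---|---|---|
| SAP 9.1, literal | Y − B1 | total |
| SAP 9.1, if Period 2 were meant | Y − B2 | total |
| Protocol 12.3.1 general rule and 12.3.2 | Y − B2 | total |
| Protocol 12.3.1, placebo-or-ivacaftor sentence | Y − B3 | increment |

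B1 and B2 both precede the Period 2 ivacaftor. The unnamed period therefore leaves open only B2 − B1, which is carryover or drift. The step from total to increment is B3 − B2, the ivacaftor response over Period 2, and only one protocol sentence takes it.

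**Size, under assumptions.** The documents give no Study 108 effects. Assume ivacaftor +4 and TEZ/IVA +6 ppFEV1 points, six equal sequences, groups defined by Period 2 treatment, and no drift. Let carryover be 20% of the Period 1 effect remaining at B2.

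- Pre-Period 1 origin: 6.0 in all three groups.
- Period 2 origin: each group loses the mean carryover of its two possible Period 1 treatments.
  - TEZ/IVA: 6 − 0.2 × (4 + 0)/2 = 5.6
  - IVA-TEZ/IVA: 6 − 0.2 × (6 + 0)/2 = 5.4
  - PBO-TEZ/IVA: 6 − 0.2 × (6 + 4)/2 = 5.0
  - With no carryover all three stay at 6.0.
- Protocol placebo-or-ivacaftor sentence, with Period 2 for TEZ/IVA: 5.6 for TEZ/IVA, 6 − 4 = 2.0 for IVA-TEZ/IVA, 6.0 for PBO-TEZ/IVA.

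With effects of 2/4, 4/6 and 6/8, the IVA-TEZ/IVA mean goes from 4, 6 and 8 to 2 each time, a shift of 2 to 6 points. Over the same cases the Period 2 reading with 20% carryover moves means by 0.2 × 2/2 = 0.2 to 0.2 × (8 + 6)/2 = 1.4.

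**Precision for scale.** With SD 15, correlation 0.90 and 227/3 ≈ 76 per group (all assumed), the 95% half-width is 1.96 × 15 × √(2 × 0.10)/√76 = 1.5 points. It is 1.1 to 1.8 for correlations of 0.95 to 0.85.

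**Covariate period alone.** Keep the change as Y − B1. Adjusting for B1 leaves a residual SD of 15 × √(1 − 0.90²) = 6.54. Adjusting for B2, which is uncorrelated with Y − B1 when all correlations are equal, leaves 15 × √0.20 = 6.71, or 2.6% more. In simulation the LS means moved by 0.01 or less.

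**The case for a change.** The best case for acting is that the conflict is textual and needs no assumed figures. Two governing documents give different baselines for every Study 108 rollover, and the 108/110 set is one of the two on which efficacy focuses. Group LS means with confidence intervals are the efficacy result here, so the absence of tests does not protect their interpretation. A 2 to 6 point difference would exceed the interval half-width, and a few sentences would remove the doubt.

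The textual difference stands. It is clearest for Study 108 placebo subjects, to whom the protocol assigns the Study 110 baseline, although with no drift the mean is 6.0 under either rule. The large shift carries less weight, because it depends on a sentence that conflicts with the general rule in Protocol 12.3.1 and with 12.3.2. Protocol 12.3.1 also allows its baseline to be specified otherwise, and section 12 leaves analysis details to the SAP.

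The missing washout reference is not good evidence of an oversight. The rules that mention a washout are keyed to the first active or first TEZ/IVA dose. A rule keyed to the first dose of any study drug needs no such qualifier, and the SAP names Period 2 where it wants Period 2.

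That the departure goes unexplained can be said only of the text available. The SAP's contents list passes from section 1 to section 3, and the SAP describes a Part A and Part B that this protocol does not contain.

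**Conclusion.** No change is needed. Read as written, SAP 9.1 gives a definite and usable rule: the value before Period 1 is the only one that precedes study drug in all six Study 108 sequences, and it gives the three groups a common origin. The protocol's specific rules would mix origins within one model. The IVA-TEZ/IVA estimate is a total change whichever Study 108 period is meant.

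What remains is small. The covariate's period has negligible effect. Study 103 contributes 23 subjects who are only summarised descriptively. SAP 9.6.2 rules out between-group hypothesis tests. An analyst would use the same pre-Period 1 value for change score and covariate and label the output accordingly. A separate table of change from the Study 110 baseline would be an optional descriptive addition; the Day 1 spirometry it would need is already scheduled.

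The numerical sizes rest on assumed treatment effects, carryover, SD and correlation. The conclusion that the SAP yields a total change rests only on the order of the three pre-dose values.

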9.2 Subject Disposition

The number and percentage (based on All Subjects Set) of subjects in the following categories will be presented:

- All Subjects Set
- Safety Set
- FAS
- Completed treatment regimen
- Prematurely discontinued treatment and the reason for discontinuation
- Completed study
- Prematurely discontinued study and the reason for discontinuation
- Subjects from each of the parent studies
- Subjects rolling over to Part B

The summary tables for these categories (except “Subjects from each of the parent studies”) based on 106/110 ES and 108/110 ES will be provided separately.

A listing of subjects who discontinued treatment or who discontinued study will be provided.

9.3 Demographics and Baseline Characteristics

The following demographic data from parent studies will be summarized separately for 106/110 ES and 108/110 ES:

- Age at screening
- Age groups (< 18, and >=18 years)
- Sex
- Ethnicity
- Race
- Geographic region by North America, Europe (including Australia and Israel)

The following baseline characteristics from parent studies will be summarized separately for 106/110 ES and 108/110 ES:

- Weight (kg)
- Height (cm)
- BMI (kg/m²)
- Weight z-score (subjects <20 years old at screening)
- Height z-score (subjects <20 years old at screening)
- BMI z-score (subjects <20 years old at screening)

- Percent predicted FEV₁
- Percent predicted FEV₁ categories (<40, ≥40 to <70, ≥70 to ≤90, >90)
- FEV₁ (L)
- CFQ-R Respiratory

Listings of informed consent, of important protocol deviations/violations will be provided. Medical history, coded by using the Medical Dictionary for Regulatory Activities (MedDRA), will not be summarized because most data were already collected in the parent studies. Only a listing will be presented for the medical history data collected in Part A.

9.4 Prior and Concomitant Medications

Medications used in this study will be coded by using the World Health Organization Drug Dictionary (WHO-DD) and categorized as:

- **Prior medication:** any medication that started before the first dose of study drug in Study Part A, regardless of when the medication ended.
- **Concomitant medication:** medication continued or newly received at, or after, initial dosing of study drug through the end of 110 TE Period.
- **Post-treatment medication:** medication continued or newly received after 110 TE Period.

A given medication can be classified as a prior, a concomitant, or a post-treatment medication; both prior and concomitant; both concomitant and post-treatment; or prior, concomitant, and post-treatment. If a medication has a missing or partially missing start/end date and it cannot be determined whether it was taken before the first dose, concomitantly, or beyond the TE period, it will be considered as prior, concomitant, and post-treatment.

Medications with missing or partially missing start dates will impute 2000 for the missing year, January for the missing month, and 1 for the missing day. Medications with missing or partially missing stop dates will impute 2050 for the missing year, December for the missing month, and the last day of the month for the missing day. The logic to decide the category of a medication is presented in Table 9-1:

Table 9-1 Logic for Determining the Category of a Medication			
Medication start date	Medication end date		
	< first dose date of 110 study drug	≥ first dose date of 110 study drug and ≤ End date of 110 TE period	> End date of 110 TE period
< first dose date of study drug	P	PC	PCA
≥ first dose date and ≤ End date of TE period	-	C	CA

> End date of TE period	-	-	A
P: Prior; C: Concomitant; A: Post			

Concomitant medications will be summarized descriptively for Safety Set by: 1) preferred name; and 2) anatomic class (ATC) level 1, ATC level 2, and preferred name.

The medications (prior, concomitant, post-treatment) will be listed.

9.5 Study Drug Exposure and Compliance

The cumulative duration of TEZ/IVA exposure based on 110 TE Period is defined as: last dose date on TEZ/IVA – first dose date on TEZ/IVA + 1 day, regardless of any interruption between the first and last dose. If the last dose date is missing, the subject’s last ETT date (for early treatment discontinuations) will be used as a substitute for analysis purposes.

Study drug compliance rate will be calculated as follows:

$$100 \times [1 - (\text{Total number of days study drug interrupted}) / (\text{Duration of study drug exposure})],$$

The total number of days study drug interrupted is defined as the sum of (number of days of study drug interrupted in each interruption interval), where number of days of study drug interrupted in each interval is defined as the interruption end date - the corresponding interruption start date + 1.

Duration of treatment and dosing compliance for Safety Set will be summarized by descriptive summary statistics: the number of subjects (n), mean, SD, median, min, and max.

Listings of study drug administration, of study drug compliance rates, and of study drug interruptions will be provided.

9.6 Efficacy Analysis

9.6.1 Definitions of Efficacy Endpoints

9.6.1.1 Absolute Change in Percent Predicted FEV1 from Baseline

ppFEV₁ is the ratio of FEV₁ (L) to the predicted FEV₁ (L), expressed as a percentage and will be calculated using the Hankinson ([1]) and Wang ([2]) standards with details in [Section 11.2](#).

9.6.1.2 Number of Pulmonary Exacerbations

The definition of a PEx is based on the definition in the individual CSP/CSR. A PEx is defined as a new or change in antibiotic therapy (IV, inhaled, or oral) for any 4 or more of the following signs/symptoms:

- Change in sputum
- New or increased hemoptysis
- Increased cough
- Increased dyspnea
- Malaise, fatigue, or lethargy

- Temperature above 38°C (equivalent to approximately 100.4°F)
- Anorexia or weight loss
- Sinus pain or tenderness
- Change in sinus discharge
- Change in physical examination of the chest
- Decrease in pulmonary function by 10%
- Radiographic changes indicative of pulmonary infection

The number of PEx is defined as the total number of PEx during the PEx Analysis Period.

